### 2. Work package 1b: Testing the psychometric properties of the aDIALOG quality of life scale

The psychometric properties of the aDIALOG scale (validity and reliability) will be tested in an exploratory validation study (cross-sectional study design), where the scale will be

administered to 120 service users. Service users will be eligible if they are aged 18 or over, have mild or moderate ID based on service records / clinical notes, are under community ID services from the East London Foundation Trust, and can provide informed verbal or written consent.

Research assistants will arrange a face-to-face meeting or conduct the assessment remotely on Teams or Zoom. We will collect basic socio-demographic data and we will ask participants to complete the aDIALOG scale, along with additional measures. In order to assess test re-test reliability, we will ask participants to complete the aDIALOG scale again on another occasion (ideally 24 hours later but no later than 1 week). This will be carried out face-to-face, online or via telephone.

### 3. Work package 2: A feasibility study of delivering aDIALOG+ in clinical services

We will conduct a single arm, uncontrolled, feasibility study of aDIALOG+ delivered by new (haven't participated in other work packages) clinicians from community ID services to assess recruitment and retention of service users and clinicians. We will recruit 8-12 clinicians, who will be eligible if they are aged 18 or over, are currently working within a community ID service, intensive support team or in a local authority or social care organisation for people with ID, are from any profession (e.g. psychology, nursing, speech and language therapy, psychiatry, social work) at grade 4 and above with a minimum of six months experience working with people with ID, consent to participate and haven't participated in other work packages.

Clinicians will administer aDIALOG+ to 3-5 service users with ID on their caseload (30 service users in total), and they will be identified through the review of medical records. Service users and their carers will then be approached by the participating clinician or CSO to take part in the study and an information sheet will be provided. Service users will be eligible if they are aged 18 or over, have mild or moderate ID based on service records / clinical notes, have a current history of behaviour that challenges (at least one incident of self-injurious behaviour, physical aggression or damage to property in the last 3 months), are living in any setting including the family home and supported living/ residential home, and can provide informed verbal or written consent. Participant carers will be eligible if they are aged 18 or over, are paid or unpaid (e.g. family carer); if a paid carer, they will need to have worked with the person for at least six months and should know the person well and support the person on a regular basis, and consent to participate. We will ask clinicians to identify and approach all the service users on their caseload, who are potentially eligible to take part, to take part in the study until they reach the recruitment target. This should reduce the likelihood of clinicians only approaching certain individuals to take part.

Clinicians will deliver aDIALOG+ using the app on a tablet (provided by the research team), once a month for six months to each of the 3-5 service users on their caseload. The tablet will be insured and it will be the research team's responsibility to provide replacements. Clinicians will receive full training (half a day), which will include the manual and will have access to online resources (including videos). Clinical supervision will be provided by their line manager as usual (at least once a month) and they will also have access to additional supervision relating to the delivery of the intervention from the research team (every 8 weeks). Assessments will be conducted at baseline and post intervention (6 months), and semi-structured interviews will be held with 6-10 clinicians, 10 service users and 10 participant carers supporting service users. Questions will be framed using the Theoretical Domains Framework, which examines issues related to implementation. Clinicians will be asked about their perspectives on the quality of training and supervision received, views

about the ease of using the app and technical challenges and practical and organisational issues (e.g. time, resources) in implementing aDIALOG+. Service users and participant carers will be asked about their views on the accessibility and ease of using the app, perceived benefits and unintended consequences of aDIALOG+, and aspects that did or did not work well and suggestions for improvements/changes. We will also ask clinicians to complete the NoMAD questionnaire (39) for assessing implementation processes.

#### 4. Work package 3: A feasibility study of aDIALOG+ in care homes

We will conduct a single arm, uncontrolled study of aDIALOG+ delivered by new (haven't participated in other work packages) care workers from care homes (supported living or residential care) for people with ID. The main aim of this study is to explore the recruitment and retention of care homes, care workers and service users, the acceptability, adherence and fidelity of aDIALOG+ delivered by care workers and completion of outcome measures. We will recruit ten care homes and their paid staff (approximately three to five staff in each care home) from East London, Bedfordshire and Cornwall. Care homes will be identified from Care Quality Commission websites and local authority and national registers. We will also use the ENRICH network (Enabling Research in Care homes) to identify care homes that are interested in research.

We will approach the service managers at the care home and seek permission for staff to take part. Care homes will be eligible if they are supported living or residential placements for service users with ID in the participating areas and the service manager has agreed for the care home to take part. Care workers will be eligible if they are aged 18 or over, have worked in the care home for at least three months, provide at least one day of support per week to service users, consent to participate and haven't participated in other work packages. Participating care workers in each of the participating care homes will receive training on how to use aDIALOG+ and will deliver the intervention using the app on a tablet (provided by the research team) to eligible service users residing in the care home. The tablet will be insured and it will be the research team's responsibility to provide replacements. Service users will be identified from service records / clinical notes by care workers, and the research team will ask staff to approach eligible service users to take part in the study. If they are interested, their details will be passed to the research team, who will contact the potential participant, provide an information sheet, and assess their eligibility and capacity to consent. Service users will be eligible if they are aged 18 or over, have mild or moderate ID based on service records / clinical notes, have a current history of behaviour that challenges (at least one incident of self-injurious behaviour, physical aggression or damage to property in the last 3 months), are residing in supported living or residential care, and can provide informed verbal or written consent. We will ask care workers to identify and approach all the service users within the care home, who are potentially eligible to take part, to take part in the study until they reach the recruitment target. This should reduce the likelihood of care workers only approaching certain individuals to take part.

Participating care workers in each of the participating care homes will receive training on how to use aDIALOG+ and will deliver the intervention using the app on a tablet (provided by the research team) to eligible service users residing in the care home. The tablet will be insured and it will be the research team's responsibility to provide replacements. Delivery will involve a 'team approach' potentially involving more than one care worker. There will be flexibility in the number of aDIALOG+ sessions that are delivered, with an expectation that it is delivered at least once a month over six months. Care workers will receive supervision from their line managers and additional supervision from the research team once every 8 weeks. Line managers will also be invited to the training session offered to the care workers,

and an additional training session can be provided regarding expectations related to their role. Additionally, the research team can offer supervision sessions for line managers once every 8 weeks, and care workers and line managers will also be able to contact the research team in between supervision sessions if they need additional support, with the option to arrange ad hoc meetings. Assessments will be conducted at baseline and post intervention (6 months), and acceptability will be assessed by carrying out focus groups at five care homes (at least 10 care workers) and interviews with 10 service users. We will also ask care workers to complete the NoMAD questionnaire (39) for assessing implementation processes.

## Data Collection

### 1. Work package 1a: Piloting adapted DIALOG+

After 4-6 weeks will invite the five clinicians, five care workers and at least ten service users to take part in separate stakeholder focus groups or interviews to obtain feedback on what aspects of the intervention (including the aDIALOG scale, app, training and manual) that worked well or did not work well and suggestions for improvement. The focus groups/interviews will be audio-recorded and transcribed. We will also ask clinicians and care workers to complete the NoMAD questionnaire (39) for assessing implementation processes from the perspective of professionals directly involved in the work of implementing complex interventions in healthcare.

**Table 1: ICONIC WP1a Piloting screening and data collection schedule**

	Completed by	Storage	Pre-consent	Consent	4-6 weeks	Ongoing or during intervention
Clinicians and care workers screened for eligibility	RT / CSO	DSH	x			
Clinician and care workers consent form	C / CW / RT / CSO	LC		x		
Service users screened for eligibility	C / CW	DSH	x			
Service users consent form	SU / RT / CSO	LC		x		
aDIALOG+ app data	SU / C / CW	ET				x
Participant withdrawal CRF	RT / CSO / SU / C / CW	LC				x
Focus group / interview audio recordings and transcripts	SU / C / CW / RT / CSO / TC	DSH			x	

NoMAD questionnaires	C / CW / RT / CSO	LC				x	
----------------------	-------------------	----	--	--	--	---	--

*Key: CW = care worker; C = clinician; CSO = clinical studies officer; DSH = data safe haven; ET = encrypted tablet; LC = (locked cabinet on ELFT property); RT = research team; SU = service user; TC = transcription company*

## 2. Work package 1b: testing the psychometric properties of the aDIALOG quality of life scale

Research assistants will arrange a face-to-face meeting or conduct the assessment remotely on Teams or Zoom. We will collect basic socio-demographic data (gender, age, ethnicity, severity of ID, neurodevelopmental conditions, day activities, living arrangements, co-morbid psychiatric and physical illnesses) and we will ask service users to complete the aDIALOG scale and the following measures (in order to assess construct and concurrent validity):

- i. Mini-MANS LD and the WHOQOL Disabilities module (measures of quality of life in people with ID) (40, 41).
- ii. Clinical Outcome in Routine Evaluation- Learning Disability (CORE-LD), 14 item version (measure of psychological distress) (42).

In order to assess test re-test reliability, we will ask service users to complete the aDIALOG scale again on another occasion (ideally 24 hours later but no later than 1 week). This will be carried out face-to-face, online or via telephone.

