Statistical analysis (work package 1b): We will examine the distribution, variability and mean/median scores for each of the items. In order to assess concurrent and convergent validity, we will examine spearman's correlation between the items relating to subjective quality of life on the aDIALOG scale and the other measures. We will assess test re-test reliability by calculating the intra class correlation coefficient (ICC). Items that show poor distribution, variability and poor test re-test reliability may be removed from the scale. We will measure the internal consistency of the items relating to subjective quality of life and the treatment aspects separately using Cronbach's alpha.

Statistical analysis (WP 2 and WP 3): The feasibility outcomes will be the main focus of analysis and descriptive statistics, with associated measures of precision appropriately accounting for clustering, will be used to assess recruitment and retention, adherence, response rates in completing the outcome measures, demographic and clinical data, and cost data. We will explore changes in the scores of the outcome measures using paired t-tests or non-parametric tests where appropriate. The primary outcome measure of changes in behaviour will be measured using the Aberrant Behaviour Checklist (ABC)- irritability subscale (43). For secondary outcomes we will measure changes in behaviour (Behaviour Problems Inventory- short form) (53), quality of life (WHOQOL Disabilities module) (40), community participation (Guernsey Community Participation and Leisure Assessment – Revised) (44), psychological distress (Clinical Outcomes in Routine Evaluation, 14 item version) (42), psychiatric disorders (Moss Psychiatric Assessment Schedule - Check) (45), global improvement (Clinical Global Impression Scale) (46), health related quality of life (modified version of the EQ-5D-3L for people with ID) (48, 49) and service use (the Client Services Receipt Inventory) (51). The frequencies of adverse and serious adverse events will also be reported.

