## **7.2 Sampling**

### **7.2.1 Size of Sample**

- Work package 1a: 5 clinicians, 5 care workers and 20 service users.
- Work package 1b: 120 service users.
- Work package 2: 8-12 clinicians, 30 service users, and 10 participant carers.
- Work package 3: 10 care homes and their care workers (3-5 care workers in each care home, approx. 40 care workers). 3-5 service users in each care home (approximately 40 service users).

Total number of participants: clinicians - 17; care workers- 45; service users- 210; participant carers- 10.

For the feasibility study there is no formal sample size calculation but the sample size would need to be sufficient in order to estimate our main parameters of interest (recruitment and retention rates) and the precision of these estimates, allowing for the clustered nature of the data (Assuming an ICC of 0.04). If we anticipate a recruitment and retention rate of 75%, 12 clinicians, and 30 service users, would allow us to estimate 95% Confidence Intervals for recruitment and retention rates with a half width of 18%.

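### WP1b lets the retest use a different mode from the first test, so the planned ICC can mix mode differences with instability and understate retest reliability

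*Protocol*

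**What the plan says.** The Study Design and Data Collection subsections for work package 1b (Protocol section 5) describe the two occasions separately.

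- First test: "Research assistants will arrange a face-to-face meeting or conduct the assessment remotely on Teams or Zoom".
- Retest: preferably after 24 hours and within one week. On mode: "This will be carried out face-to-face, online or via telephone".

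Neither subsection says that the two modes should agree. Table 2 shows item scores collected at baseline and at follow-up and does not mention mode.

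Under Data Storage and Analysis, test-retest reliability is to be assessed by an ICC, with no reference to mode. The result then feeds a decision about content: "Items that show poor distribution, variability and poor test re-test reliability may be removed from the scale". Section 7.2.1 gives the size as "Work package 1b: 120 service users", with no precision target for the ICC.

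**The concern.** A test-retest ICC is read as the stability of a scale when the same person answers under the same conditions a short time apart. The short interval limits real change, so what remains is meant to be measurement error. If the conditions also change, the disagreement contains a second component, the difference between modes, and a single pair of scores cannot tell the two apart.

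The protocol itself makes a mode effect plausible in this population. Section 1 reports that the response format and language of the existing scale were judged too complex. Section 2 lists linguistic limitations and sight and hearing impairment among the barriers to digital interventions. Section 6 says that aDIALOG+ sessions will be held in person, so telephone is not the mode in which the intervention will use the scale.

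Testing the psychometric properties of aDIALOG is a principal objective (section 4.1, objective 2). At stake are the reported reliability of the scale and, item by item, one of the inputs to decisions on which items to keep.

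**Working it through.** **What is permitted**

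| First test | Retest | Same mode? |
|---|---|---|
| In person | In person | Yes |
| In person | Online or telephone | No |
| Video | Online by video | Yes |
| Video | In person or telephone | No |

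A telephone retest never has a matching first test. The other mismatches are possible but not inevitable.

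**Size**

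The protocol states no ICC target, precision or cut-off for work package 1b, so there is no figure to reproduce. What follows is illustrative, and every input is an assumption:

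- *c*: the ICC if both tests used the same mode, with total variance set to 1
- *f*: the share of pairs that change mode
- *v*: mode-by-person variance as a fraction of total variance
- *d*: mean shift between modes, in SD units

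The mean squared difference between the two scores is D = 2(1 − c) + f(v + d²), and the observed agreement ICC is

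ICC = c / (c + D/2) = c / [1 + ½ f (v + d²)].

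With f = 0.5:

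- c = 0.80, v = 0.1, d = 0: 0.80 / (1 + 0.25 × 0.10) = 0.80 / 1.025 = 0.78
- c = 0.80, v = 0.3, d = 0.3: 0.80 / (1 + 0.25 × 0.39) = 0.80 / 1.0975 = 0.73
- c = 0.70, v = 0.1, d = 0: 0.70 / 1.025 = 0.68
- c = 0.70, v = 0.3, d = 0.3: 0.70 / 1.0975 = 0.64

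With f = 0.2 and the same two pairs of v and d:

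- c = 0.80: 0.80 / 1.01 = 0.79 to 0.80 / 1.039 = 0.77
- c = 0.70: 0.70 / 1.01 = 0.69 to 0.70 / 1.039 = 0.67

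With f = 0, or with v = d = 0, the observed ICC equals c.

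A separate two-occasion simulation agrees with the formula. For c = 0.75, f = 0.5, d = 0.3 and v = 0.09 it gave an agreement ICC of 0.718; the formula gives 0.75 / (1 + 0.25 × 0.18) = 0.718. The consistency form of the ICC gave 0.726. That form is less affected by a mean shift, and not at all if everyone shifts equally, but it does not remove mode-by-person differences.

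**Against sampling error**

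On Fisher's z scale with two occasions, the standard error is about 1/√(n − 1.5). For an ICC of 0.70, z = 0.867.

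- n = 120: half-width 1.96/√118.5 = 0.180, giving about 0.60 to 0.78
- n = 96 (20% of pairs mixed and set aside): half-width 0.202, giving about 0.58 to 0.79
- n = 60 (half set aside): half-width 0.256, giving about 0.54 to 0.81

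The assumed bias of 0.02 to 0.06 at f = 0.5 is smaller than the sampling half-width at n = 120. Unlike sampling error, it runs in one direction and does not shrink with more participants.

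**The case against.** **Flexibility may be deliberate.** The study is described as exploratory, the retest window is short, and allowing any mode plausibly protects retest completion. This stands, and it argues against banning telephone retests. It does not argue against preferring a matched mode where one can be arranged.

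**The bias may be small.** With few mixed pairs or a weak mode effect it is a hundredth or two, well inside sampling error. This also stands. The documents do not allow the size to be fixed.

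**An analysis plan could deal with it.** It could choose the form of the ICC and stratify by mode, and the case report forms, which are not shown, may already record mode. But no analysis can supply a same-mode pair for someone retested by telephone. The matching rule belongs to data collection.

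**Stronger readings that the documents do not support.** A reader might infer that sound items will be dropped because of the telephone. The removal rule lists poor distribution, variability and poor retest reliability together and leaves removal to discretion, so on a literal reading a low ICC alone need not remove an item. A reader might also try to count the items affected. That would need an ICC cut-off, which the protocol does not state, and the number of items and response options in aDIALOG, which it does not give: the eleven items and seven points belong to the original DIALOG. Finally, a reader might assume that the adapted response format cannot be presented in a telephone assessment. The adapted format is not described, and nothing rules out the participant having the scale to hand.

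**Conclusion.** The point holds as a design weakness. The protocol permits unmatched modes, makes a mismatch certain for every telephone retest, and plans an ICC that cannot separate mode from instability. Retest reliability can therefore be biased downward, in an estimate that serves a principal objective and helps inform item removal.

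Its size is unknown. A fall from 0.80 to 0.78-0.73, or from 0.70 to 0.68-0.64, rests on half the pairs being mixed, mode-by-person variance of 10-30% and a mean shift of up to 0.3 SD. With 20% mixed, the same effects give 0.79-0.77 and 0.69-0.67. If mode has no effect, there is no bias. The case for change is that the source of error is avoidable at very little cost; the documents do not show that the damage would be large.

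**What to change.** In the work package 1b text of section 5:

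1. State that the retest uses the same mode as the first test, and that a different mode, including telephone, is used only when the same mode cannot be arranged within the one-week window.
2. Record the mode at both occasions.
3. Report the ICC for same-mode pairs alongside the ICC for all pairs.
4. State that no item is removed for poor retest reliability that appears only when mixed-mode pairs are included.

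The cost is a few sentences, one form field if mode is not already recorded, and some scheduling effort, with possibly a few later or lost retests. The interval for the same-mode ICC is slightly wider if mismatches are uncommon. It would be clearly wider if half the pairs were mixed, which is why matching at data collection matters more than restricting the analysis afterwards, and why both ICCs should be shown.

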**Table 2: ICONIC WP1b Psychometric testing screening and data collection schedule**

	Completed by	Storage	Pre-consent	Consent	Baseline	Follow up (24 hours to 1 week)	Ongoing or during intervention
Service users screened for eligibility	C	DSH	x				
Service users consent form	SU / RT / CSO	LC		x			
Service user questionnaire	RT / CSO / SU	LC			x		
aDIALOG+ item scores	RT / CSO / SU	LC			x	x	
Participant withdrawal CRF	RT / CSO / SU	LC					x

*Key: C = clinician; CSO = clinical studies officer; DSH = data safe haven; LC = (locked cabinet on ELFT property); RT = research team; SU = service user*

### 3. Work package 2: A feasibility study of delivering aDIALOG+ in clinical services

If service users are interested in taking part, the CSO or study research assistant will contact the person and their carer to discuss the study, will assess eligibility, obtain consent and conduct a baseline assessment, which will include completion of a socio-demographic and clinical data collection form (gender, age, ethnicity, severity of ID, neurodevelopmental conditions, day activities, living arrangements, co-morbid psychiatric and physical illnesses, prescribed medication (e.g. psychotropic medication), and psycho-social interventions that they have received or are receiving (e.g. positive behavioural support). Demographic information will also be collected from clinicians participating in the study (gender, age, ethnicity, profession, number of years in the service and years' experience working with people with ID) and participant carers (gender, age, ethnicity and education level). The aDIALOG+ app will capture data on the number of times aDIALOG+ was administered, changes in the aDIALOG scale scores over the duration of the intervention and goals set, but does not collect any identifiable information about the patients it is used with. Data on the number of sessions attended will be used to assess adherence to the intervention; we will analyse the mean changes in the scores for each domain on the aDIALOG scale.

